## If **Yes**, respond to the following:

b. For Tufts Medical Center studies:

Check to see if all software applications used in this study are already on the list of approved software. Please review the version type and/or described use-case of each application to confirm approved use. If the software you are using is not already on the list of approved software (or will not be used in accordance with the approval details on the list), you are required to complete this IT Security form so Tufts Medical Center can review the security of the software.

LI Check this box if the II Security form has been completed and submitted.
$\square$ Check this box if you have confirmed that the software applications used in this study are
already on the list of approved software (and will be used in accordance with the details on
the list)

c. For Tufts University studies:

Check to see if all software applications used in this study are already on the list of approved software. If the software you are using is not already on the list of approved software (or will not be used in accordance with the approval details on the list), Information Security review is needed.

☐ Check this box if Information Security review is needed.

☑ Check this box if you have confirmed that the software applications used in this study are already on the list of approved software (and will be used in accordance with the details on the list)

of Ve	eterinary Medicine
□Ye	es 🛮 No
If Ye	es, respond to all of the following:
	Describe the nature of the data/specimens to be transferred: GI luminal content and stool amples
	State to whom or what entity the data/specimens will be transferred: [name] at Fufts Veterinary School.
Γ	Explain how data and/or specimens will be transported (e.g. fax, mail, delivery, email, etc.): [name] or her designee will courier the stool samples and recovered mini-pills to [name] laboratory at the Tufts School of veterinary Medicine, Grafton Campus.
	Confirm that you have consulted with Tufts MC Grants & Contracts
( . L	[contact] ), Tufts University Technology Transfer , or CGH/MWH Legal Counsel to determine whether an agreement is needed to permit the ransfer of data/specimens, and one of the following is true:
	i. $\square$ An agreement (e.g. contract, Clinical Trial Agreement, Collaboration Agreement, Data Use Agreement (DUA), or Material Transfer Agreement (MTA)) has been or will be established that will cover any transfer of data/specimens, and the agreement will be executed prior to any transfer.
	ii. □ Grants & Contracts, Technology Transfer, or Legal Counsel has determined that an agreement is not needed for this research. (The appropriate office listed above should make this determination, not the Investigator.)
	iii. $\boxtimes$ A determination from the appropriate office is still pending. (The study cannot be approved by the IRB until the appropriate office makes a determination, but it can be approved prior to the execution of an agreement.)

7. Will data (or specimens) be sent outside of Tufts Medicine or Tufts University and/or sent

between Tufts Medicine and Tufts University? Samples will be sent to Tufts University School

- 8. Will you use the Tufts Medicine electronic medical record system EPIC for this study? 

  ☑ No
- **9.** Explain whether audio/videotapes and/or photographs of subjects could potentially identify the study subject. If so, indicate who will have access to (be able to view) these items, in addition to the research team, how long the videotapes or photographs will be retained for the study, and what the plan is for their destruction: 

  N/A
- 10. Check to confirm that study records will be retained for the timeframe described in the record retention policy of the "SOP Records Retention Timeframe Investigators".
- 11. \(\infty\) Check to confirm that you will follow the "Confidentiality and Data Security Guidelines for Electronic Research Data" for collecting, storing, transferring, and securing electronic data. If not, describe how your plan differs from these guidelines and what steps that will be taken to secure the data (e.g., training, authorization of access, password protection, encryption, physical controls, and separation of identifiers and data) during storage, use, and transmission:
- 12. A Certificate of Confidentiality will be issued (for NIH studies) or obtained: ⊠ N/A

## F.4. Provisions to Protect the Privacy Interests of Subjects

1. Describe the steps that will be taken to protect subjects' privacy interests (e.g. ensuring that discussion of the study will take place in a private area where subjects cannot be overheard):

The consent interview will take place in a private room in the HNRCA MRU. Family members will accompany Non-English-speaking subjects.

2. Describe the steps that will be taken to make the subjects feel at ease with the research situation in terms of the questions being asked and the procedures being performed. "At ease" does not refer to physical discomfort, but the sense of intrusiveness a subject might or might not experience in response to questions, examinations, and procedures (e.g. ensuring that subjects are comfortable with the research team members performing the study procedures): Subjects will have at least 90 minutes to review the study documents and consider whether they wish to participate. It will be emphasized that study participation is entirely optional. Additionally, subjects' comfort during questions and research procedures will be ensured by clarifying each step of the process and easing any potential concerns they may have with regards to privacy and the research study process. The HNRCA MRU staff has extensive experience in this area and understanding the importance of subject comfort in terms of psychological well-being, study compliance and study retention.

# F.5. Data Management

1. Describe the data that will be collected during the study and how the data will be obtained including what source records will be used (submit all surveys, scripts, and data collection forms.): The data generated as part of this proposal will consist of primary data spanning several types of digital formats dependent on the method of data generation. Anthropometric and blood pressure measures will be recorded in a clinical research management system and provided as deidentified and coded spreadsheets for analyses. Gut microbiome sequences will be stored in fastq format on the Tufts University research computer cluster. GI and serum metabolite measures, cardiometabolic risk factors and all other measurements will be stored as numeric spreadsheets. Due to the varied nature of the data associated with this proposal, the use of several open file types will be necessary to ensure the data is both machine readable, and readily accessible and usable for the greater scientific research community. To that end, all data files will be stored in open formats such as TIFF for the image files, and comma-separated values (csv) files for spreadsheet data.

Additionally, plain text readme and metadata files will be developed and included with the study data to provide supporting documentation and descriptions of data collection methods. These will include abbreviations, coded values and other conventions used when recording the data. The supporting documents will be configured in a way that provide all the information necessary for independent investigators to use, validate and understand the data associated with this proposal.

- a. If there are plans for long-term follow-up (once all research related procedures are complete), describe the data will be collected during this period:  $\boxtimes$  N/A
- 2. Describe the data management plan including the data types (e.g. biomarker, imaging, clinical events, etc.) and amount (n participants) of data, how data are collected (e.g. REDCap) and processed (e.g. analysis of imaging), any specialized data tools and software and code, and who will be responsible to monitor compliance with this plan: All research data will be stored on either the secured, internal HNRCA network storage assigned to the research group or REDCap. Access to data is restricted based on study and team role and controlled through robust user- and role-based access rights. All access to identifying information is recorded and logged. Two-factor authentication is enabled and required in order to access research data and individual staff undergo training in data security best-practices.

3. Describe any procedures that will be used for quality control of collected data: Review of data by PI.

## F.6. Provisions to Monitor the Study to Ensure the Safety of Subjects

- 1. Describe the plan to periodically evaluate the data regarding both harms and benefits to assess subject safety as follows:
  - a. The data that will be reviewed, including safety data, untoward events, and efficacy data: The study subject will be monitored for discomfort during the study visit and will be accompanied at all times by a research team member. There are no medically anticipated immediate adverse effects associated with the assessments (height, weight, waist circumference, blood pressure) taken at the study visit, with consumption of the food items, or oral ingestion of the mini-pills.

Who will review the data: The study doctor will evaluate any GI or other issues reported by participants. An independent physician, [name]. Professor of Medicine and Nutrition, Tufts Medical Center/Tufts University will act as Safety Monitor and will review AEs and SAEs, if they occur and sign off on annual safety reports to the NIH.

- b. How the safety information will be obtained and documented (e.g., case report forms, by telephone calls with participants, printouts of laboratory results, etc.): Any instances of GI discomfort/side effects self-reported by participants to MRU staff via phone or at an inperson visit will be documented in REDCap.
- c. The frequency of data collection, including when safety data collection starts: If nursing staff determine a report is an AE or has potential of being an AE, the study doctor will review and the PI or designee will be sent a summary of the complaint/issue by email on the day the report has been made to the IRB and Safety Monitor.
- d. *The frequency or periodicity of review of cumulative data*: Yearly.
- e. The statistical tests for analyzing the safety data to determine whether harm is occurring: N/A
- f. Any conditions that trigger an immediate suspension of the research or other action for the research: N/A
- g. Describe the entity responsible for monitoring the data, and their respective roles (e.g., the investigators, the research sponsor, a coordinating or statistical center, an independent medical monitor, a Data and Safety Monitoring Board (DSMB) /Data Monitoring Committee (DMC), and/or some other entity, and the timeframe for reporting events to this entity: The study doctor will monitor any GI or other issues reported by participants. The Safety Monitor will review AEs and SAEs and sign off on annual safety reports to the NIH.
- **2.** A copy of the DSMB/DMC Charter if the study is enclosed with the submission: N/A

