- 4. Specify if first time study device will be used in humans: This is the first time this speicifc 3D printed mini-pill device will be tested in humans. However, a similar NSR device, albeit larger (NCT05749068), has been tested in humans after receiving IRB approval at another institution (See Supplements 5 and 6). 
- 5. Is there an active control group?

☐ Yes No

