There are no major risks associated with the short-term consumption of the meat containing entrées. Prior work has reported no adverse effects from consumption of the plant-based meat alternatives. 16 Some of the plant-based alternative entrées contain gluten, so participants with known sensitivity to gluten will be excluded. There are no known risks associated with obtaining the study measures (height, weight, waist circumference and resting blood pressure). There might be some discomfort from fasting for 8 to 10 hours prior to the study visits. There may be some nausea associated with swallowing the 6 mini-pills. The need to collect and return multiple stool samples at the end of each diet phase, may be inconvenient for the participants. There is a low risk of sensitivity to Betty Crocker Classic Gel Food Color, which contains Blue 1. Most allergic reactions to blue dyes are mild, described as grade I (69– 87%) and present with urticaria (itchy skin), pruritus (hives), and/or generalized rash.  To address this issue participants with known sensitivity to food coloring will be excluded. Additionally, the nursing staff will monitor participants after ingestion of the pills and dye for any possible symptoms. There may be a small amount of bruising and discomfort, and rarely infection, associated with the drawing of blood samples. Subjects may become light-headed and faint. Every effort will be made to minimize discomfort to study subjects, with experienced nursing staff performing the blood draws. No known psychological or social risk are anticipated. There are no economic risks as study entrées will be provided to the study subjects, and there is no cost associated with the mini-pills. Protected health information will be collected as part of this study. Study participants may face risks related to inadvertent release of confidential information. This risk will be minimized through careful adherence to best practices for data collection and management. All research staff will be trained in principles and methods for assuring participant confidentiality and safety. Data will be used only in aggregate and no identifying

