Week 1\_Day 1: Following the screening visit, participants will come to the HNRCA after an 8 to 10 hour fast to return their stool sample. They will then be given the opportunity to review and sign the Study Informed Consent form and also be given the option to review and sign the Optional Tissue Banking Informed Consent form. Once enrolled, participants will have their weight, waist circumference, and blood pressure measured and provide a fasting blood sample. They will meet with a registered dietician to review instructions for entrée storage/consumption and pick up diet phase I specific entrées and checklist.

Week 2\_ Day 8: Participants will come to the HNRCA to pick up another week of study entrées and also return and review their Entrée Checklist with a registered dietician.

*Week 2-Day 14:* Participants will come to the HNRCA after an 8 to 10 hour fast to provide a fasting blood draw. They will be given a breakfast containing a study entrée specific to the diet phase to be consumed within 30 minutes, and then asked to swallow 6 mini-pills along with blue dye dispersed in ½

\*\*The number of stool samples to be collected will vary depending on mini-pill recovery

cup of water within 15 minutes. Additional water may be consumed, if desired. Participants will be given study entrées for another week and stool collection kits with cooler and instructions.

*Week 3-Days 15 to 21:* Participants will continue to consume 2 entrées per day until the mini-pills are eliminated in the stool, which can vary between 2 and 4 days, but can be up to 6 days. Participants will be asked to collect and return all stool samples produced every 48 hours, until they are informed by study staff that all pills have been recovered.

Participants can stop consuming the entrées once all mini-pills are recovered. There will be a 2 week break at this point during which participants will have no study obligations and can consume their normal diet. If all of the mini-pills are not recovered after 6 days, participants can stop consuming the study entrees, and we will conduct a 2-week follow up telephone call to inquire about symptoms or concerns.

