a. How individuals will be screened for eligibility. Specify screening that will take place prior to informed consent and screening that will take place after informed consent: IRB approved telephone prescreening questionnaire will be used to determine eligibility based on inclusion and exclusion criteria (see sections C.1 and C.2). Participants who meet prescreening criteria will be invited to the HNRCA for a screening visit to confirm eligibility. At the screening visit,

after obtaining consent, BMI will be confirmed by direct measurement of height and weight. In addition, blood pressure will be measured, and medical history/medication use and dietary habits will be reviewed.

- b. *Procedures being performed to monitor subjects for safety or to minimize risks:* Every effort will be made to minimize discomfort to study subjects, with experienced nursing staff performing the blood draws and monitoring mini-pill ingestion. Post ingestion of the minipills, all participants will receive a 2 week follow up telephone call. During this call, we will review medical history in order to monitor any possible longer-term side effects including urgent/emergency visits, or hospitalizations specifically for abdominal pain/discomfort, GI obstruction, perforation, diverticulitis, GI bleeding.
  - c. All drugs and devices used in the research, their regulatory approval status (whether they are approved by the FDA and being used within their FDA approved indication), and the purpose of their use. For drugs, specify the dosage of each drug, how they will be administered, and how often they will be administered. For devices, specify how they will be used/implanted:

The mini-pill is a size 2 pill. It is not a wearable. It is not an implant. The mini-pill does not deliver any drugs. It is not intended for diagnosis or treatment. It is a passive, single-use, ingestible collection device that is recovered from the stool and its contents will be analyzed for microbial communities inhabiting the GI lumen. See Supplement 3 (Ingestible Mini-pill for Collection of GI Tract Luminal Content) which provides a detailed description, images, dimensions, designs and the safety profile of the device from both materials and our recent animal studies in hounds. An image of the pill is shown below.

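### Between the ingestion visit and the two-week call, GI symptoms after this first-in-human device are captured only by self-report, with no systematic pre-ingestion record to compare them with

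*Protocol*

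**What the plan says.** Section B.2 item 4 states: "This is the first time this speicifc 3D printed mini-pill device will be tested in humans". Section B.3 foresees a tolerability problem: "There may be some nausea associated with swallowing the 6 mini-pills".

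The provisions for finding symptoms are spread over several sections:

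- **At the ingestion visit.** Under B.3, nursing staff watch participants after the pills and dye. Under F.6 item 1a, participants are monitored for discomfort during the visit.
- **General route.** Under F.6 item 1b, what goes into REDCap is "Any instances of GI discomfort/side effects self-reported by participants to MRU staff via phone or at an inperson visit". Item 1c asks when safety data collection starts and how often it takes place; the answer covers only how a report is handled once made.
- **Two-week call.** The safety-monitoring item of E.2 says "all participants will receive a 2 week follow up telephone call", and that in the call "we will review medical history in order to monitor any possible longer-term side effects including urgent/emergency visits, or hospitalizations" for named GI events. The Week 3 and Week 8 descriptions in E.2 give a call only where some mini-pills are still missing after 6 days: "we will conduct a 2-week follow up telephone call to inquire about symptoms or concerns".
- **Before ingestion.** The Day 14 and Day 49 descriptions run from fasting blood draw to a "breakfast containing a study entrée specific to the diet phase", then to six mini-pills with blue dye. Neither these descriptions nor Table 1 includes a symptom assessment.

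**The concern.** Transit is expected to take 2 to 4 days and may take up to 6. For most of that time the participant is at home. Samples go back every 48 hours and staff tell participants when all pills are recovered, so contact exists, but the protocol attaches no symptom question to it. A mild or short-lived complaint enters the record only if the participant raises it.

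Every ingestion also follows two weeks on a study diet and comes straight after a diet-specific meal. A complaint on Day 15 may reflect the diet, the breakfast, the dye or the pills. Without the same questions put to the same person just before ingestion, there is no systematic same-diet comparator.

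What is at stake is the tolerability evidence for a device new to humans. The only safety endpoint in H.1 is recovery of the 12 mini-pills, so the symptom record carries the rest. B.3 itself supports the device's safety partly by citing the absence of reported adverse events with a similar device. A comparable statement from this trial will be only as strong as the method of asking.

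**Working it through.** The protocol gives no symptom rate and no capture share, so there is no planned figure to reproduce. The main check is to line up the windows.

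| Window | Capture described | Gap |
|---|---|---|
| Diet weeks before ingestion (Days 1–14, 36–49) | Self-report by phone or at visits (F.6 1b) | No systematic record |
| Ingestion visit (Days 14, 49) | Nurse monitoring (B.3, F.6 1a) | No pre-ingestion symptom record |
| Transit at home, 2 to 6 days | Self-report (F.6 1b) | No solicited question |
| Two weeks after ingestion | Telephone call (E.2) | Worded around longer-term effects and urgent care; who is called is stated in two ways |

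The weak window is transit, and the missing comparator is the record just before ingestion.

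To show what incomplete capture could mean, take:

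- n = 30 completers (H.2), counted as persons, not ingestions;
- c = share of affected participants whose symptom is recorded; 100%, 50% and 25% are assumptions;
- p = true proportion with a given mild symptom; 10% is an assumption.

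**Upper limit after zero recorded events.** The one-sided 95% limit for the recorded proportion is 1 − 0.05^(1/30) = 0.095. The recorded proportion is p × c, so the limit for p is 0.095 / c:

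- c = 1: 9.5%
- c = 0.5: 0.095 / 0.5 = 19%
- c = 0.25: 0.095 / 0.25 = 38%

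**Chance of recording nothing when p = 10%.** This is (1 − 0.10 × c)^30:

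- c = 1: 0.90^30 = 0.04
- c = 0.5: 0.95^30 = 0.21
- c = 0.25: 0.975^30 = 0.47

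These figures show direction and rough size only. They apply to mild symptoms that depend on self-report, not to events seen by the nurses or likely to surface in the two-week call.

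**The case against.** The strongest reply is that capture is not passive throughout. Nurses supervise ingestion and watch for symptoms afterwards. The foreseen nausea is tied to swallowing the pills, which happens under observation, and an early dye reaction would be covered in the same way. E.2 also provides a call to all participants that covers abdominal pain or discomfort, obstruction, perforation, diverticulitis and GI bleeding. This stands. A reader might infer that the whole trial relies on spontaneous report, or that a low event count would be uninterpretable; the protocol supports neither. What remains is the interval between leaving the visit and the call, and a call framed around longer-term effects and urgent care is poorly suited to mild symptoms that have already passed.

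A reader might also infer that device effects cannot be separated from diet effects at all. That goes too far. The device is given in both phases, so the meat versus plant-based comparison is not confounded with it. Complaints volunteered before ingestion are recorded by the same route, and onset relative to ingestion is informative. The supportable statement is that the separation is not reliable without a systematic record.

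Finally, case report forms or a call script not shown here may contain symptom questions. The protocol points to none for the transit window, and F.6 answers the question of how safety information is obtained with self-report. This concerns data collection that the protocol itself fixes, not analysis detail that could be left to a statistical analysis plan.

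**Conclusion.** The point holds in a limited form. After the supervised ingestion visit and until the two-week call, self-report is the only described route for GI symptoms, and no systematic symptom record precedes ingestion on Days 14 and 49. Mild or transient symptoms during transit may be under-counted, and effects of the ingestion day cannot be reliably separated from the background of being on a study diet.

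The size is not known. Under the assumed capture shares of 50% and 25%, zero recorded events in 30 people would be compatible with true rates up to about 19% and 38%, against 9.5% with full capture. The change is worth making before enrolment, because a missing pre-ingestion answer cannot be recovered later.

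The two accounts of the two-week call contradict each other. The difference matters, because it decides whether every participant is actively asked at least once after going home.

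**What to change.** Amend F.6 items 1b and 1c, Table 1 and the Day 14 and Day 49 procedures as follows:

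1. Add one short fixed symptom list built from events the protocol already names: nausea, abdominal pain or discomfort, GI bleeding, and itching or rash.
2. Ask it on Days 14 and 49 before breakfast and ingestion, and at each existing stool return until the pills are recovered. State this as the start and frequency of collection in item 1c.
3. Report new or worsened symptoms against the same person's pre-ingestion answer, by diet phase.
4. State the limit of this comparison: it separates background symptoms on the diet from the ingestion-day package, but not breakfast, dye and pills from each other, because they are taken together.
5. Reconcile the Week 3 and Week 8 descriptions in E.2 (call if pills are not all recovered) with the E.2 safety-monitoring item (call to all participants).

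The cost is a few minutes at contacts that already exist and one REDCap form. The downside is that more mild events will be recorded and need review.
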